### **2.2 Primary**

Conduct a randomized comparative study of DVT prophylaxis using either standard IPC (Group 1) or the RF MAC system (Group 2) in 300 patients after TJR surgery.

Hypothesis 1: Study participants who use the RF MAC will have rates of adherence to wear time of a fully operational device that are at least 25% higher than those using standard IPC devices.

Hypothesis 2: Patients wearing the RF MAC in the first 24 hours following surgery will take at least 25% more steps as measured by an activity tracker than those patients using standard of care IPC devices.

Hypothesis 3: Patients who use the RF MAC will have a mean gait speed at 14 postoperative days that is at least 20% higher than patients receiving standard of care as measured by the 4-meter walk test.

Hypothesis 4: The time required for preparing patients to ambulate will be 50% less using the RF MAC than standard IPC devices.

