In the first 24 hours post-operative, the Research Coordinator will record the total number of minutes that the DVT prevention device (control or intervention) was properly applied to the patient's lower extremities and fully operational. For Group 1, this information will be collected via patient interview and Research Coordinator observation. The Research Coordinator will visit the patient at least two (2) times in the first 24 post-operative hours and visually observe if the DVT devices are on the patient as directed by the standard of care, are fully operational and are correctly positioned. The Research Coordinator will note visual observations for each visit in the CRF. In addition, the Research Coordinator will ask the patient if they have kept their DVT devices on as directed by the healthcare team. The patient's response will be recorded on the CRF.

For Group 2, the MAC System will automatically capture time in use and display results on the device. Following the same protocol, the Research Coordinator will visit Group 2 patients at least two (2) times during the 24 post-operative period to observe if the RF MAC is in use, properly positioned (the device will not operate unless it is properly positioned) and will record the time displayed for DVT prophylaxis on the patient's CRF. In addition, the Research Coordinator will ask the patient if they have kept the DVT devices on as directed by the healthcare team. this information and results will be captured from the device display by the Research Coordinator and recorded in REDCap.

For both groups, steps in the first 24 hours will be measured using an activity tracker and the Research Coordinator will record this information in REDCap. For patients in Group 2, steps will also be measured automatically by the RF MAC System. The Research Coordinator will read the display screen on the MAC and record steps taken during the first 24 post-operative hours.

For both groups, at least once each day during the in-patient period, the Research Coordinator will measure through observation and using a stopwatch, the amount of time required by a nurse or other healthcare worker to prepare the patient to ambulate (removing DVT prophylaxis tubes, cords, etc.). The purpose of ambulation, time required to prepare the patient and time required to return the DVT prophylaxis will be recorded on the CRF.

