Group 2 will receive instructions on how many hours per day to use the RF MAC System and a targeted number of steps to achieve per day (from healthcare team). Primary compliance data will be self-reported and collected by the Research Coordinator. Data related to mobility goals will also be collected with the activity tracker. A secondary method of data collection will be the RF MAC System itself. At the end of each day, patients in Group 2 will record the data on the display of the RF MAC System screen, filling in the data for each category in a paper diary provided by the Research Coordinator (provided to Coordinators by Recovery Force). The paper diary will include an image of the screen and users will write the data they see on the screen at the end of each day.

The Research Coordinator will call each participant (in both groups) two times a week during the two-week study. Telephone calls will focus on 1) reminding patients to comply with orders; 2) reminding patients to wear their activity tracker; and 3) reminding patients to comply with DVT prevention orders. The Research Coordinator will answer any questions and confirm the participants are complying with study requirements. The Research Coordinator will also review with the patient the return procedures for the RF MAC, which will involve bringing the device with them to their two-week post-operative office visit.

The patients in both groups will be reminded the day before their 2-week appointment via a telephone call to bring their activity tracker with them to their appointment. The patients in Group 2 will be reminded to also bring back the RF MAC System in its entirety with them to their appointment.

At the 2-week follow up appointment, the Research Coordinator will conduct a final 4-meter walk test. Results will be recorded on the patient's CRF in REDCap.

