Once the walk test is complete, the Research Coordinator will direct the patient to complete a final survey. Next, the patients will return all study equipment (activity tracker and the RF MAC System) to the Research Coordinator. Patients who return all equipment will receive their \$100 remuneration for study participation. Renumeration will be reduced by 50% to \$50.00 for any patients who do not return their equipment. Patients who did not return the devices will receive a postage-paid package for returning both the activity tracker and RF MAC device to Recovery Force. Once the equipment has been received by Recovery Force, the additional \$50 remuneration will be mailed to the participant. In addition, participants at Tufts Medical Center will receive \$21 stipend as reimbursement for parking costs.

Research Coordinators will also send at-home physical therapists of individuals in Group 2 a link to a brief survey about the RF MAC.

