## **2.5 Study Duration**

The total duration of the study is expected to be 18 months (site training, recruitment, enrollment, participation, case closeout, analysis, completion of final report). This study will include two groups. Group 1 will serve as the control group and will receive standard care. Group 2 is the intervention group and will receive standard care and the proposed intervention, the RF MAC System. Group 1 will consist of 75 patients at each of two sites (total of 150 patients). Group 2 will consist of 75 patients at each of two sites (total of 150 patients). Patients will be assigned to a group by a site Research Coordinator using a random numbers generator at their final pre-operative appointment.

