# 8 ADVERSE EVENT REPORTING

## 8.1 Non-Device-Associated Adverse Events

Adverse events occurring during the enrollment period should be documented by the Investigator in progress notes but will not be collected or analyzed by Recovery Force unless considered serious.

Serious adverse events (SAEs) encountered during study enrollment will be documented by the Investigator and reported to Recovery Force immediately upon discovery. SAEs are defined under current Good Clinical Practice (cGCP) guidelines as events that result in one or more of the following:

- life-threatening illness or injury;
- permanent impairment of a body structure or a body function;
- medically necessary in-patient hospitalization;
- medical or surgical intervention necessary to prevent permanent impairment to body structure or function; or
- fetal distress, fetal death, or congenital abnormality.

SAEs will be reported using an Unanticipated Adverse Device Effects (UADE) form which serves the dual role of capturing pertinent SAE information per industry guidelines and capturing device

information pertinent to medical device standards. Other serious events that affect the rights, safety, or welfare of subjects must also be documented on the UADE form and must be reported immediately to Recovery Force and to the Investigator's IRB according to that IRB's policies.

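### No post-surgery contact is described as asking about adverse events, and the reporting window in 8.1 is undefined, so capture of events at home is passive

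*Combined protocol and SAP*

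**What the plan says.** **Reporting rule.** Section 8.1 states: "Serious adverse events (SAEs) encountered during study enrollment will be documented by the Investigator and reported to Recovery Force immediately upon discovery". Non-serious events within the enrollment period go into the investigator's progress notes, and the sponsor neither collects nor analyzes them. Neither enrollment term is defined or given an end date. The same section requires other serious events affecting subjects' rights, safety or welfare to be documented and reported, and 8.2.2 requires reporting of unanticipated adverse device effects (UADEs). Neither of those duties is limited to enrollment.

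**Meaning of enrollment.** Section 2.4 (In-Patient) places enrollment and randomization at the pre-operative appointment. Section 2.5 lists the study's stages as "site training, recruitment, enrollment, participation, case closeout, analysis, completion of final report", with enrollment and participation as separate items.

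**Contacts.** In hospital, the coordinator checks the device and, beyond that, "the Research Coordinator will ask the patient if they have kept their DVT devices on as directed by the healthcare team". After discharge, "The Research Coordinator will call each participant (in both groups) two times a week during the two-week study". On content: "Telephone calls will focus on 1) reminding patients to comply with orders; 2) reminding patients to wear their activity tracker", with a third reminder about DVT prevention orders. The rest of the call is described as follows: "The Research Coordinator will answer any questions and confirm the participants are complying with study requirements". At 2 weeks there is a walk test, a survey and return of equipment. For equipment not brought back: "Patients who did not return the devices will receive a postage-paid package for returning both the activity tracker and RF MAC device to Recovery Force".

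**Analysis.** Section 7.1 plans no tabulation of adverse events.

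**The concern.** A duty to report an event once it is discovered is not a method of discovering it. The schedule brings the coordinator into contact with every patient several times, yet the stated content of each contact is device status, mobility, compliance or logistics. A patient treated at another hospital during the second week would not, on the plan as written, be asked about it.

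The window adds to the problem. A site that takes enrollment to mean the pre-operative act could stop recording before the at-home phase. A site that takes it to mean time on study would not. The two sites could therefore apply different rules.

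What is at stake is the reading of the safety result. Section 1.1 presents DVT as the most feared complication of joint replacement, and prophylaxis at home differs by group: Group 1 may have stockings, standard IPC or no orders, while Group 2 uses the RF MAC. The plan also hypothesizes that "Patients wearing the RF MAC in the first 24 hours following surgery will take at least 25% more steps", so falls are a natural item to count beside steps. The documents give no fall rate, and nothing here shows that falls would rise. But with no question asked, few reported events could mean few events or few reports.

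**Working it through.** No figure in the plan bears on this point. The one design calculation, 130 per group in 7.1, concerns continuous outcomes. The check is a listing of contacts and clauses.

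**Step 1. Post-surgery contacts, both groups**

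| Contact (2.4) | Number per patient | Stated content | Adverse event question described |
|---|---|---|---|
| In-hospital visits, first 24 hours | at least 2 | device position and operation, whether kept on, wear time, steps | none |
| Pre-discharge test | 1 | walk test, step count; device display and survey (Group 2) | none |
| Calls at home | 2 per week × 2 weeks = 4 | three reminders, questions answered, compliance, return procedure | none |
| Call the day before the visit | 1 | bring the equipment | none |
| 2-week visit | 1 | walk test, survey, equipment return | none |

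Total: 2 + 1 + 4 + 1 + 1 = at least 9 per patient, counting the reminder call as separate from the four. None has a described event question. Section 2.3 limits the patient-reported outcomes to comfort, acceptance and ease of use.

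**Step 2. Opportunities already planned**

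At full enrollment of 300:
- Regular calls: 4 × 300 = 1,200.
- Reminder calls: 1 × 300 = 300.
- Final visits: 1 × 300 = 300.

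Dropout, which 7.1 puts at up to 15%, would lower these counts. They measure opportunities, not missed events.

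**Step 3. Share of follow-up at home**

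The anticipated stay is 48 hours or less, so (14 − 2)/14 = 12/14 = 86%.

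**Step 4. Which duties reach the home period**

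| Duty | Limit stated | Clearly covers home? |
|---|---|---|
| Adverse events in progress notes (8.1) | enrollment period, undefined | no |
| SAEs to the sponsor (8.1) | study enrollment, undefined | no |
| Other serious events (8.1) | none | yes |
| UADEs (8.2.2) | none | yes |

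All four depend on someone learning of the event.

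**Step 5. Differences between groups in chances to report**

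The patient packet with a list of study contacts is specified only for Group 2 (Synopsis and 2.4). The survey of home physical therapists is specified for Group 2 in 2.4; the Synopsis names no group.

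**Step 6. Illustration only; the risks and capture rates are assumptions**

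- *Incomplete capture.* With a true SAE risk of 1% to 5%, 300 patients have 300 × 0.01 = 3 to 300 × 0.05 = 15 events. If 30% to 60% were captured, the reported count would lie between 3 × 0.30 = 0.9 and 15 × 0.60 = 9.
- *Unequal capture.* With the same 3% risk in both groups, each group of 150 has 150 × 0.03 = 4.5 events. Capture of 30% in one and 60% in the other gives 1.35 and 2.7 reported, a twofold difference from reporting alone.

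**The case against.** The strongest case on the other side is that the plan has more safety coverage than its contact list shows.

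- **Other routes to discovery exist.** A reader might infer that serious events at home surface only if the patient volunteers them. The documents do not support that. The 2-week contact is a post-operative office visit, patients come from the investigators' own clinics (3.2), and both groups have home physical therapy orders for at least 14 days. Section 4.1.2 tells device users with pain, swelling or unusual reactions to see their physician. This stands. These routes are still incidental: none has a described path into the study record.
- **The window may be only loose wording.** A reader might infer that 8.1 excludes events at home. Taken that literally, it would stop before any device was used, which would defeat its purpose. Section 2.4 also uses the word loosely: it refers to the tracker as provided at enrollment, yet hands it out on the day of surgery. The list in 2.5 describes project stages, not a safety window. This too stands: the fault is ambiguity, not exclusion.
- **Late returners are contacted.** A reader might infer that patients who keep the RF MAC after the visit have no further contact. They receive a return package, and the remaining $50 is mailed once the equipment arrives.
- **The groups are closer than they look.** A reader might count the Group 2 diary and device return as extra occasions to report. The Synopsis gives Group 1 a journal too, and Group 1 returns a tracker and receives the same calls. Only the differences in Step 5 remain.
- **Leaving non-serious events uncollected is a stated choice.** That is so, and a fall leading to hospitalization already meets the SAE definition. The choice does not supply a way of finding serious events, and changing it has to be done openly.
- **Absence is hard to prove.** The survey items, the CRF, the site protocols in Appendices A and B, and Section 8.3 (by its title a contact for SAE reporting) were not in the text reviewed. An event question there cannot be ruled out.

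**Conclusion.** The point holds as a gap in ascertainment. In the protocol text, none of at least nine post-surgery contacts per patient is described as asking about adverse events. The two main reporting clauses in 8.1 rest on an undefined window with no end date, while about 86% of the 14 days fall at home. Capture at home is therefore passive, may be incomplete and may differ by group, and few reported events could not be read as safety.

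The documents do not show that events will be missed, or how many; Step 6 is illustration only. The conclusion assumes that stays run to the anticipated 48 hours or less, and that no event question sits in the survey, CRF or appendices. The four efficacy hypotheses are unaffected. The change is worth making because the contacts needed are already planned.

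**What to change.** 1. **Section 8.1, window.** Replace both enrollment terms with one defined window: consent through the 2-week visit or device return, whichever is later.
2. **Section 2.4, questions.** Add one short fixed question set, identical in both groups and with a CRF field: any fall, new leg swelling or pain, unplanned medical visit or readmission, or skin problem. Ask it at the in-hospital visits, the existing calls and the 2-week visit, and enclose it with the device-return mailing.
3. **Section 8.1, non-serious events.** Amend the sentence under which the sponsor does not collect or analyze these events, so that the listed items are collected. This reverses a stated choice and should be presented as such.
4. **Section 7.1, analysis.** Tabulate each item by randomized group, with the number of patients actually asked as the denominator.
5. **Survey, CRF and appendices.** If they already hold an event question, cite it in 2.4 and confirm that it is the same for both groups.

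The cost is about one CRF page, one table and brief added time at contacts already planned, with no new visits. More events will be recorded in both groups. The change concerns data collection only and leaves clinical management as it is.

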## **2.5 Study Duration**

The total duration of the study is expected to be 18 months (site training, recruitment, enrollment, participation, case closeout, analysis, completion of final report). This study will include two groups. Group 1 will serve as the control group and will receive standard care. Group 2 is the intervention group and will receive standard care and the proposed intervention, the RF MAC System. Group 1 will consist of 75 patients at each of two sites (total of 150 patients). Group 2 will consist of 75 patients at each of two sites (total of 150 patients). Patients will be assigned to a group by a site Research Coordinator using a random numbers generator at their final pre-operative appointment.

# **3 STUDY POPULATION**

## **3.1 Sample Size and Target Study Population**

The following vulnerable patients will be excluded from the study: pregnant women, prisoners, homeless and cognitively impaired. Data will be collected at two locations, one site for each cohort.

Each of the two study sites are responsible for recruiting participants in the study (150 total participants, with 75 in each of two study groups).

### **3.3 Patient Selection**

The eligibility criteria for prospective enrollment of subjects are shown in **Table 1**.

**Table 2: Inclusion/Exclusion Criteria for Enrollment of Subjects**

Inclusion	This study will be conducted on adult volunteers, aged 40-85 years who speak English.
Exclusion	The following vulnerable patients will be excluded from the study: pregnant women, prisoners, homeless and cognitively impaired. Individuals who do not speak English will be excluded from this study.

## **4 STUDY MATERIALS**

### **4.1 Investigational Products and Accessories**

#### **4.1.1 RF Movement and Compressions (MAC) Device**

The RF MAC Device is a novel device that is applied to the lower legs of patients that provides intermittent active compressions to the calf muscles which results in increased blood flow in the veins, moving blood towards the direction of the heart and reducing the risk of clot formation.

The Movement and Compressions System is intended to be a portable and wearable system, prescribed by healthcare professionals, to treat the following conditions by stimulating blood flow in the legs:

- Aid in the prevention of DVT (deep vein thrombosis);
- Enhance blood circulation;
- As a prophylaxis for DVT by persons expecting to be stationary for long periods of time.

During use, the system also monitors patient orientation and movement. It allows healthcare providers and users to implement individualized patient management plans for DVT prophylaxis and patient mobility protocols by utilizing data accumulated by the patient on the previous day as a benchmark. The data displayed on the device allows providers to monitor the patient's orientation and activity, which can be used to identify risk factors for hospital-acquired events linked to immobility such as: deep vein thrombosis, pressure ulcers, pneumonia, atrophic muscles, and delirium.

The device can be used in the home or clinical setting. The device is intended for use in an adult patient population.

#### **4.1.2 RF Movement and Compressions (MAC) Device Safety and Handling Issues**

The Recovery Force MAC System consists of three components: the strap, designed for single patient use; and the controller, designed for multi-use, and the charging hub. If you are, or may be, pregnant, do not use. Recharge battery using an outlet readily accessible for quick disconnect. Do not use where aerosol (spray) products are being used or oxygen is being administered.

Electromedical devices have the potential for explosion in these situations. Never use pins or other metallic fasteners with this product as these could damage the wiring of the device. Care must be taken when operating this equipment around other equipment to avoid reciprocal interference.

Potential electromagnetic or other interference could occur to this or to the other equipment. Try to minimize this interference by not using other equipment in conjunction with this device. Keep and store when not in use out of reach of children, pets, pests, and away from water. No modification of this equipment is allowed. No user serviceable parts inside. If you experience pain, swelling, sensation changes, discomfort or any unusual reactions (including allergic reactions to the materials in this device) while using the device, stop using the device and consult your physician immediately. If pulsing or throbbing occur, the device may be wrapped too tightly. Loosen immediately. This device should not be used adjacent to or stacked upon other devices.

### **4.2 Other Study Materials**

Study notebooks to maintain study documents, including signed Informed Consents and all applicable information, and additional forms to be collected and retained by the study institution during the course of the study and maintained for three (3) years following the study completion date.

## **5 STUDY PROCEDURES**

### **5.1 Study Data**

Eligible subjects will be invited to participate in the study using a convenience sampling strategy. Potential subjects must provide informed consent to participate. To be eligible for participation, subjects must speak English and be between the ages of 40-85.

